## 16.6 Appendix 6: List of idiosyncratic drug reactions (IDRs) for investigators

**Table 16-7 Definition of potential idiosyncratic drug reactions**

Reaction	Possible events diagnoses and signs/symptoms
Anaphylaxis	Anaphylactic/anaphylactoid reactions
Angioedema: diagnosis and/or signs and symptoms	Angioedema, site specific angioedema urticaria, anisarca/generalized edema urticaria
Severe skin reactions	Acute generalised exanthematous pustulosis, Cutaneous vasculitis, Drug reaction with eosinophilia and systemic symptoms (DRESS), Epidermal necrosis, Toxic skin eruption , Oculomucocutaneous syndrome, Skin necrosis, Stevens-Johnson syndrome (SJS), Toxic epidermal necrolysis (TENS)
Agranulocytosis and other cytopenic events	Agranulocytosis, aplastic anemia, pancytopenia
Other hypersensitivity reactions	Other suspected hypersensitivity to suspected drug
Liver reactions	Any event that qualifies as a liver laboratory trigger or event as defined in Appendix 2
While this list is intended as a guide to the investigator, other potential IDRs may arise.

FDA	Food and Drug Administration
IgE	Immunoglobulin E
ICS	Inhaled Corticosteroid
LABA	Long Acting Beta-2 Agonist
MedDRA	Medical Dictionary for Regulatory Activities
PDS	Programming dataset specification
PT	Preferred term
SoC	System organ class
o.d.	Once a day
PK	Pharmacokinetic
QTc	Corrected QT interval
SAE	Serious Adverse Event
SAF	Safety analysis set
SOC	System Organ Class

1 Introduction

This document contains details of the statistical methods that will be used in the phase II clinical trial CQAW039B2201. This study is designed to evaluate the pharmacokinetics, safety and tolerability of fevipiprant delivered via once daily chewable tablet (CT) in children aged 6 to <12 years with asthma.

The study was terminated by sponsor prematurely on December 16, 2019. Decision was taken to discontinue Study CQAW039B2201 based on evaluation of the QAW039 (fevipiprant) development program in asthma including results from the recently completed LUSTER-1/-2 (CQAW039A2307/A2314) studies. The last Patient Last Visit, LPLV, was on January 22, 2020. All patients from Cohort A completed the study. 5 subjects of Cohort B were treated, none of them completed the trial and none reached scheduled Day 8 visit.

This statistical analysis plan is an abbreviated approach of presenting the limited data collected in the study and does not reflect the full analysis scope described in Section 12 of the study protocol (Version 01, Amendment 1 to original protocol released on 13-Feb-2019). Important information is given in the following sections and details are provided, as applicable, in section 5: [Appendix](#).

1.1 Study design

[figure not shown]
This study uses a multicenter, open-label design to assess the pharmacokinetics, safety, and tolerability of fevipiprant CT in children aged 6 to < 12 years with asthma (figure 1-1). The study includes an 4-8 day, open-label treatment period in which subjects receive fevipiprant CT once daily (o.d.) in addition to their rescue medication (e.g. short-acting β -agonists [SABAs]) and potentially standard-of-care (SoC) asthma therapy (inhaled corticosteroids [ICS] with or without an additional controller therapy).

There will be 2 treatment dose cohorts studied (fevipiprant 75 mg o.d. and one higher dose selected based on PK obtained at 75 mg/day, [e.g. 150, 225, 300, or 375 mg once daily]). Within each dose cohort, subjects will be stratified approximately 1:1 ratio into 2 age groups: ages 6 to < 9 years and ages 9 to < 12 years.

Six subjects will be included in Cohort A and 6 to 18 subjects in Cohort B. Approximately 20 subjects will need to be screened in order to include 12 subjects into the treatment period (screen failure rate ~40%). After the interim analysis, additional subjects may need to be recruited so that total number of subjects completing treatment is maximum 24, in this case approximately 40 subjects will need to be screened. It is intended that 12 to 24 patients will complete the study. Dropouts, non-completers and patients who are not eligible for PK assessment at End of treatment (e.g. because they did not take study drug for 3 consecutive days prior to EOT visit) will be replaced. Detailed information regarding sample size calculation is provided in [section 3](#).

A planned interim analysis will be conducted to support decision making when 6 subjects (3 subjects from each of the 2 age strata) receiving the 75 mg dose level complete the treatment and provide the planned PK and safety data. At interim analysis, safety, as well as mean and variability of PK data of the 75 mg dose level will be assessed to have the right dose and number of subjects for the higher dose at the second stage. For detailed information, please refer to [Section 3](#).

Figure 1-1 Study design

*Cohort B will be at 225 mg CT o.d. or at a different dose (e.g. 150, 300 or 375 mg)

1.2 Study objectives and endpoints

Section 2 of the study protocol lists the following primary and secondary objectives.

Table 1-1 Objectives and related endpoints

Objective(s)	Endpoint(s)
Primary objective(s)	Endpoint(s) for primary objective(s)

 To determine the key pharmacokinetic parameters of fevipiprant at steady state (ss), 	
 Area under the curve (AUC_{0-24h,ss}), maximum plasma concentration (C_{max,ss}),

Objective(s)	Endpoint(s)
after at least four consecutive days of dosing	and oral clearance (CL/F)
Secondary objective(s)	Endpoint(s) for secondary objective(s)

 To evaluate the urinary excretion of fevipiprant and CCN362 at steady state To evaluate the safety & tolerability of fevipiprant over treatment period To evaluate the pharmacokinetics of CCN362, the major metabolite of fevipiprant at steady state To evaluate additional pharmacokinetic parameters of fevipiprant at steady state 	
 CLr, amount and fraction of dose excreted over the PK collection interval Safety laboratory values (including peripheral blood eosinophils), vital signs, ECG, adverse events C_{max,ss}, time of maximum plasma concentration (T_{max,ss}), AUC_{0-24h,ss}, minimum plasma concentration (C_{min,ss}) of CCN362 T_{max,ss}, C_{min,ss}, (CL/F)/kg of fevipiprant

2 Statistical methods

2.1 Data analysis general information

The final analysis will be performed [REDACTED]. The most recent version of SAS available in the statistical programming environment [REDACTED] will be used for the analysis.

2.1.1 General definitions

2.1.1.1 Study day

Study day will be defined as the number of days since the date of first dose of study treatment. The date of first dose of study treatment will be defined as Day 1 and the day before the first dose of study treatment will be defined as Day -1.

Therefore, for a particular date, study day will be calculated as follows:

- for dates on or after the first date of study treatment,
Study day = Assessment date – Date of first dose of study treatment + 1;
- for dates prior to the first date of study treatment,
Study day = Assessment date – Date of first dose of study treatment.

If a patient has not taken study treatment, the date when the study treatment has been assigned, will be used instead of the date of first dose of study treatment. Then, the date when the study treatment has been assigned is defined as Day 1 and the day before is defined as Day -1.

2.1.1.2 Baseline definition

For baseline assessments, checks will be performed to ensure the assessments were indeed taken prior to the first dose of study treatment. If baseline assessment (as mentioned in below

table) is missing or not confirmed to be pre-dose, the last value taken at any scheduled or unscheduled visit before the first administration of study treatment will be used for baseline. Otherwise, the baseline will be set to missing without imputation.

Parameter	Baseline assessment
Laboratory data (hematology, biochemistry)	Screening visit
Vital signs (body temperature, pulse rate, systolic and diastolic blood pressures)	Treatment Day 1 Pre-dose
Height, weight and BMI	Screening visit
ECG	Screening visit

2.1.1.3 Post-baseline measurement

Post-baseline measurements are defined as those assessments after the first dose of study treatment. When change from baseline is of interest the following formula will be used for each scheduled visit and time-point where baseline and post-baseline values are both available: Change from baseline = post-baseline value – baseline value.

2.2 Analysis sets

The following analysis sets are defined:

- The Safety Set will consist of all patients who received at least one dose of study treatment including non-eligible patients who received study treatment in error. Patients will be analyzed according to the treatment they received. The safety set will be used in the analysis of all safety variables.
- The PK analysis set will include all subjects with at least one available valid (i.e. not flagged for exclusion) PK concentration measurement, who received any study drug and with no protocol deviations that impact on PK data. Patients will be analyzed according to the treatment they received.

2.3 Patient disposition, demographics and other baseline characteristics

2.3.1 Patient disposition

For treatment epoch, the overall number of patients who entered, completed, and discontinued that phase will be summarized including the reasons for discontinuation.

The number of patients included in each analysis set will be tabulated.
Protocol deviations as well as reason for exclusion from analysis sets will be listed.

2.3.2 Patient demographics and baseline characteristics

Demographic and baseline characteristics measured including age, age stratum (6 to <9 years and 9 to <12 years), gender, race, ethnicity, height, weight and body mass index (BMI) will be summarized by cohort on safety analysis set.

Continuous variables will be summarized using descriptive statistics (mean, median, standard deviation, minimum, and maximum) and categorical variables will be summarized in terms of the number and percentage of subjects in each category.

Medical history will be coded with the Medical Dictionary for Regulatory Activities terminology (MedDRA) using the most recent version at the time of database lock. Verbatim recorded history/conditions will be listed together with the coded terms, date of diagnosis/surgery and whether the problem was ongoing at start of the study.

2.4 Treatments (study treatment, rescue medication, concomitant therapies, compliance)

2.4.1 Study treatment / compliance

Dosage and date of administration at clinic (Treatment Day 1 and End of Treatment (at steady state)) and at home (1 day prior End of Treatment e.g. treatment Day 7) will be listed for all subjects in safety set.

2.4.1.1 Duration of exposure

Duration of exposure to study treatment will be calculated as the number of days starting from the first dose date up to and inclusive the last dose date. The duration of exposure will be summarized by cohort for the safety set as a continuous variable with the standard descriptive statistics.

2.4.2 Prior, concomitant and post therapies

Prior and concomitant medications will be listed on the Safety set.

2.5 Analysis of the primary objective

2.5.1 Primary endpoint

The primary objective of the study is to determine the pharmacokinetics of fevipiprant based on AUC_{0-24h,ss}, C_{max,ss} and CL/F.

The AUC_{0-24h,ss}, C_{max,ss} and CL/F for fevipiprant at steady state after at least four consecutive days will be the primary variables. PK analysis set will be used for analysis of all PK parameters. Due to termination of study no PK data of Cohort B are available, thus all summaries of PK data will be done for Cohort A only.

2.5.2 Statistical hypothesis, model, and method of analysis

The primary variables, AUC_{0-24h,ss}, C_{max,ss} and CL/F will be analyzed by standard non-compartmental analysis and summarized for Cohort A, through descriptive summary statistics (including mean, SD, CV% mean, Geometric mean, CV% geometric mean, median, minimum and maximum).

Plasma concentrations will be assessed at EOT visit (pre-dose, 0.5, 1, 2, 3, 5, 8h) and will be expressed in mass per volume units. All concentrations below the lower limit of quantification (LLOQ) or missing data will be labeled as such in the concentration data listings. Concentrations below the limit of quantification will be treated as zero in summary statistics and for the calculation of parameters and the pre-dose concentration on EOT visit will also be used as 24 h concentrations to derive AUC_{0-24h,ss}.

2.5.3 Handling of missing values/censoring/discontinuations

Subjects with no valid PK concentration measurements, will be excluded from the analysis. Under missing completely at random assumption, subjects included in the analysis will be considered as representative of all subjects received treatment. Drop-outs and non-completers will be replaced.

No other methodology is planned to address missing data.

2.5.4 Supportive and Sensitivity analyses

Not applicable

2.6 Analysis of the secondary objectives

The secondary endpoints will be analyzed as described below.

2.6.1 Safety analyses

All safety evaluation will be based on the safety set.

2.6.1.1 Adverse events (AEs)

All adverse events including asthma exacerbations will be coded with MedDRA using the most actual version at the time of database lock. AEs (including asthma exacerbations) starting on or after the time of the first intake of study drug and until the 7 days (30 days for SAEs) after the last intake of study drug will be classified as a treatment-emergent AEs. Any AEs that started during the study after signing informed consent and before the time of the first intake of study drug will be classified as prior AEs and will not be included in tabulations of treatment-emergent AEs.

The number and percentage of patients who reported treatment-emergent adverse events will be summarized by primary system organ class (SOC), preferred term (PT), and cohort for all adverse events by maximum severity

Unless otherwise specified, primary system organ classes will be sorted alphabetically and, within each primary system organ class, the preferred terms will be sorted in descending order of frequency in Cohort A. If a patient reported more than one adverse event with the same preferred term, the adverse event will be counted only once for that preferred term level. If a patient reported more than one adverse event within the same primary system organ class, the patient will be counted only once at the system organ class level.

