### **Screening Period (Screening to Treatment Visit)**

Within 14 days prior to treatment visit or at Screening Visit, written informed consent from the parent(s)/legal guardian(s), and subject assent (if applicable), will be obtained before any study-related assessments or procedures are performed. The subject's participation in the trial must be documented in the subject's medical record and all study related evaluations performed at each visit must be clearly documented in source documentation and on electronic case report forms (eCRFs).

Study sites should check the interactive response technology (IRT) for subject age cohort availability before Screening Visit begins. If the subject qualifies, Screening Visit can proceed with the documentation of demographic data, the assessment of study inclusion/exclusion criteria, and past/current medical history. The subject can then be entered into the IRT system to continue screening.

Once IRT has confirmed subject participation, physical and laboratory assessments may be performed ( [Section 8.4](#) ). At this visit, subjects will be instructed to withhold any prohibited medication as applicable ( [Table 6-3](#) ) prior to Treatment Visit (Day 1). The window between Screening Visit and Treatment Visit Day 1 (Screening Period) is up to 14 days.

Throughout the study (from Screening Visit through Follow-up period), subjects will continue to receive their rescue medication (e.g. SABA) and potentially SoC asthma therapy which could be ICS with or without additional controller medication. Leukotriene receptor-antagonists (LTRAs) must be stopped at Screening Visit and in that case ICS should be initiated or up-titrated to the next higher dose as per investigator's judgement; this change of treatment should be allowed to stabilize during the 14 days Screening Period. LTRAs treatment can be continued after End of Treatment (EOT) as per investigators decision.

Rescue medication such as SABAs will not be provided in this study, but may be prescribed by the investigator and used as needed.

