### **10.1.2 Serious adverse events**

An SAE is defined as any adverse event [appearance of (or worsening of any pre-existing)] undesirable sign(s), symptom(s) or medical condition(s) which meets any one of the following criteria:

- fatal
- life-threatening

Life-threatening in the context of a SAE refers to a reaction in which the subject was at risk of death at the time of the reaction; it does not refer to a reaction that hypothetically might have caused death if it were more severe (please refer to the ICH-E2D Guidelines).

- results in persistent or significant disability/incapacity
- constitutes a congenital anomaly/birth defect
- requires insubject hospitalization or prolongation of existing hospitalization, unless hospitalization is for:
  - routine treatment or monitoring of the studied indication, not associated with any deterioration in condition
  - elective or pre-planned treatment for a pre-existing condition that is unrelated to the indication under study and has not worsened since signing the informed consent
  - social reasons and respite care in the absence of any deterioration in the subject's general condition
  - treatment on an emergency outsubject basis for an event not fulfilling any of the definitions of a SAE given above and not resulting in hospital admission
- is medically significant, e.g. defined as an event that jeopardizes the subject or may require medical or surgical intervention to prevent one of the outcomes listed above

Medical and scientific judgment should be exercised in deciding whether other situations should be considered serious reactions, such as important medical events that might not be immediately life threatening or result in death or hospitalization but might jeopardize the subject or might require intervention to prevent one of the other outcomes listed above. Such events should be considered as "medically significant". Examples of such events are intensive treatment in an emergency room or at home for allergic bronchospasm, blood dyscrasias or convulsions that do not result in hospitalization or development of dependency or abuse.

All malignant neoplasms will be assessed as serious under "medically significant" if other seriousness criteria are not met.

Any suspected transmission via a medicinal product of an infectious agent is also considered a serious adverse reaction.

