### **10.1.3 SAE reporting**

To ensure subject safety, every SAE, regardless of causality, occurring after the subject has provided informed consent and until 30 days following the last administration of study treatment must be reported to Novartis safety within 24 hours of learning of its occurrence. Detailed instructions regarding the submission process and requirements are to be found in the investigator folder provided to each site.

Consider the following 2 categories to determine SAE reporting timeframes:

1. Screen Failures: SAEs occurring after the subject has provided informed consent until the time the subject is deemed a Screen Failure must be reported to Novartis.
2. Enrolled and/or Treated Subjects: SAEs collected between time subject signs ICF until 30 days after the subject has discontinued or stopped study treatment.

All follow-up information for the SAE including information on complications, progression of the initial SAE and recurrent episodes must be reported as follow-up to the original episode within 24 hours of the investigator receiving the follow-up information. An SAE occurring at a different time interval or otherwise considered completely unrelated to a previously reported one must be reported separately as a new event.

If the SAE is not previously documented in the Investigator's Brochure or Package Insert (new occurrence) and is thought to be related to the study treatment, a Novartis Chief Medical Office and Patient Safety (CMO&PS) Department associate may urgently require further information from the investigator for health authority reporting. Novartis may need to issue an Investigator Notification (IN) to inform all investigators involved in any study with the same study treatment that this SAE has been reported.

Suspected Unexpected Serious Adverse Reactions (SUSARs) will be collected and reported to the competent authorities and relevant ethics committees in accordance with EU Guidance 2011/C 172/01 or as per national regulatory requirements in participating countries.

Any SAEs experienced after the 30 day period after the last study visit following the last administration of study treatment should only be reported to Novartis Safety if the investigator suspects a causal relationship to study treatment.

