#### **Adverse events**

AEs (including asthma exacerbations) starting on or after the time of the first intake of study drug and until the day after the last intake of study drug will be classified as a treatment-emergent AEs. Any AEs that started during the study after signing informed consent and before the time of the first intake of study drug will be classified as a prior AEs and will not be included in tabulations of treatment-emergent AEs.

Treatment-emergent AEs will be summarized, by system organ class and preferred term, overall by system organ class, preferred term and maximum severity, suspected drug-related AEs by system organ class and preferred term. Treatment-emergent SAEs will be summarized, by system organ class and preferred term. The summarization will be provided by cohort.

If a subject reported more than one AE with the same preferred term, the AE will be counted only once. If a subject reported more than one AE within the same primary system organ class, the subject will be counted only once at the system organ class level.

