2.6.1.3 ECG

ECG measurements include ventricular rate, QT interval, RR interval, PR interval, QRS duration, and Fridericia's QTc (calculated as $QTcF = QT / \sqrt[3]{RR}$ (in seconds), where $\sqrt[3]{}$ denotes the cube root).

ECG data measured more than 7 days after last dose of study treatment are regarded as post treatment data and will not be summarized. All data will be included in the analyses regardless of rescue medication use. All data will be listed.

- The number and percentage of patients with newly occurring or worsening notable QTcF values (see [Section 5.5](#) for definition of notable values) summarized by cohort at any time on treatment considering all post-baseline data from scheduled, unscheduled and premature discontinuation visits

The same approach as for notable laboratory values will be used to define a newly occurring notable QTc value and a worsening notable QTc value.

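### Treatment-emergent adverse events are defined by start time only, so an event that begins before dosing and worsens on fevipiprant can drop out of the maximum-severity table

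*SAP*

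**What the plan says.** SAP 2.6.1.1 counts as treatment-emergent those events "starting on or after the time of the first intake of study drug and until the 7 days (30 days for SAEs"), with those days counted from the final dose. Any post-consent event starting "before the time of the first intake of study drug will be classified as prior AEs and will not be included in tabulations"; the tables meant are the treatment-emergent ones. Protocol 12.5.1 uses the same starting point, "starting on or after the time of the first intake of study drug", with a shorter end of window: "until the day after the last intake of study drug will be classified as a treatment-emergent AEs". SAP section 4 records a change to this definition, but only to the end of the window.

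The one clinical adverse event table in SAP 2.6.1.1 shows treatment-emergent events by maximum severity. The registry tables in SAP 2.6.1.1.1 are also described as treatment-emergent.

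Other parts of the plan take account of worsening. SAP 2.6.1.3 counts "newly occurring or worsening notable QTcF values", and SAP 2.6.1.2 and 2.6.1.4 do the same for laboratory values and vital signs. The definition of a serious event in protocol 10.1.2 covers "appearance of (or worsening of any pre-existing") signs, symptoms or conditions.

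**The concern.** An adverse event is not fixed at its onset. A mild event that begins in screening can become severe during dosing, and that change is what a table of on-treatment maximum severity should display. Under a rule based on start time, the change has no effect on classification.

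The window before dosing is not empty in this trial. Screening lasts up to 14 days, and for children on leukotriene receptor antagonists these "must be stopped at Screening Visit and in that case ICS should be initiated" or up-titrated (protocol section 3, Screening Period). Some symptoms could therefore begin between consent and first intake and still be present on Day 1.

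The protocol describes this as the first safety experience with fevipiprant in this age group, and safety over the treatment period is a secondary objective. With so few children dosed, a single unreported worsening would visibly change the table.

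**Working it through.** The plan gives no figure to reproduce. The check sets the rules side by side, applies them to one hypothetical event, and then works out the weight of one child.

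**How an event is recorded**

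- Protocol 10.1.1 asks for severity, start and end dates, and seriousness as items of an adverse event record. It does not ask for the date on which severity changed.
- Nothing in either document tells sites to open a new record when a non-serious event worsens.
- Protocol 10.1.3 says that "progression of the initial SAE and recurrent episodes must be reported as follow-up to the original episode". This applies once an event is already serious.
- SAP 5.1.2 leaves imputation of event dates to a programming specification that is not among the documents.

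**Hypothetical event: mild on Day -3, ongoing at first intake, severe on Day 3**

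| How the site records it | Start date used | Class under SAP 2.6.1.1 | In maximum-severity table? |
|---|---|---|---|
| One record, severity updated | Day -3 | Prior | No |
| Second record for the worsening | Day 3 | Treatment-emergent | Yes |
| Separate asthma exacerbation beginning on drug (protocol 8.4.4) | Day 3 | Treatment-emergent | Yes |

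The result turns on a recording choice that the plan does not settle. In the first row no other specified output recovers the event. SAP 2.6.1.2 to 2.6.1.4 promise listings of all laboratory, ECG and vital-sign data, but SAP 2.6.1.1 has no equivalent for adverse events.

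**Weight of one omitted child**

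Inputs: Cohort A has 6 children (the planned number in SAP 1.1, assumed equal to the number treated; SAP section 1 says all of Cohort A completed). Cohort B has 5 treated (SAP section 1).

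Change in the observed proportion = 1/n.

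- Cohort A: 1/6 = 16.7 percentage points
- Cohort B: 1/5 = 20.0 percentage points
- Both cohorts: 1/(6 + 5) = 1/11 = 9.1 percentage points

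Each exceeds the top of the 0 to 5% range from which SAP 2.6.1.1.1 will take the registry cut-off for non-serious events. A single child would therefore be enough to bring a term into that table.

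**The case against.** The strongest reply is that the plan may already capture worsening through separate records. The registry counting rule in SAP 2.6.1.1.1 expects consecutive records for the same child and term, at most a day apart, that can differ in severity or seriousness. If sites work that way, the on-treatment record has its own start date and is counted. A defined asthma exacerbation arising on drug can likewise be a new event. This stands as a reason why the loss may not happen. It does not supply a rule that prevents it.

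A reader might infer that such an event is also certain to vanish from the serious-event table. The documents do not support that. The follow-up rule in protocol 10.1.3 concerns progression of an event that is already serious, so it does not fix the start of one that first becomes serious on drug. The same section has a serious event in a different time interval reported as new, and protocol 10.1.2 treats worsening of an existing condition as capable of being a serious event. Serious events are reported to the sponsor from consent onward in any case, so the gap is in tabulation only.

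A reader might also gauge the risk from the share of days before dosing: 14/(14 + 8) = 64% to 14/(14 + 4) = 78%. That is not a risk. It assumes the longest screening period and ignores the follow-up window. With 7 more days it is 14/29 = 48% to 14/25 = 56%. With 30 more, for serious events, it is 14/52 = 27% to 14/48 = 29%. Most screening-onset events never worsen and are rightly excluded.

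Nor do the documents show that worsening asthma is the likeliest event. The number of children taking leukotriene antagonists is not given, inhaled corticosteroid is started or raised when they stop, and eligibility and adverse events are reassessed on Day 1 before dosing.

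Finally, the laboratory, ECG and vital-sign rules compare measurements with a baseline. They show a different approach to worsening, but they do not contradict an onset rule for event records.

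**Conclusion.** The point holds for severity. Read literally, SAP 2.6.1.1 leaves on-treatment worsening of a screening-onset event out of the maximum-severity table whenever the site keeps one record, and no specified listing would show it. For the registry table of serious events the same loss is possible but not established.

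The exposed group is narrow: the event must begin after consent, be ongoing in a child who is still dosed, and then worsen. How many such events there were, if any, cannot be told from the documents. The size is therefore conditional: one affected child is 16.7 points in Cohort A, given six treated, or 20 points in Cohort B. For on-treatment severity the omission can only lower the count. The table is descriptive and no inferential result depends on it.

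**What to change.** Change the SAP only. The study has been terminated and its last visit is past, so rewording the protocol would achieve nothing. Before database lock:

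1. In SAP 2.6.1.1, define an event as treatment-emergent if it starts, or if an event with pre-dose onset increases in severity or becomes serious, on or after first intake and within the stated window (7 days after last intake, 30 for serious events).
2. Tabulate such an event at its maximum severity on treatment.
3. Review each pre-dose-onset record among the dosed children for later changes in severity or seriousness. The record items do not include a date of worsening, so a site query may be needed.
4. List prior adverse events with start date, severity and seriousness.
5. Note the change in SAP section 4 with the existing change to the window.

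The cost is one clause, one listing and a short review across 11 children (6 + 5). Treatment-emergent counts may rise slightly and may include worsening that follows leukotriene antagonist withdrawal rather than fevipiprant. Without a control group the table cannot separate the two, but the listing would show the pre-dose onset.
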